## Follow-up of unresolved adverse events

Adverse events will be followed until resolution or until the investigator determines that the adverse event is not expected to return to baseline.

The following variables will be collected for each AE:

AE (verbatim)

The date when the AE started and stopped

NCI CTCAE grade and the maximum CTC grade attained

Whether the AE is serious or not

Investigator causality rating against the Investigational Product (yes or no)

Action taken with regard to investigational product/comparator/combination agent Outcome.

In addition, the following variables will be collected for SAEs:

Date AE met criteria for serious AE
Date Investigator became aware of serious AE
AE is serious due to
Date of hospitalization
Date of discharge
Probable cause of death
Date of death
Autopsy performed

Description of AE

Causality assessment in relation to Study procedure(s)

Causality assessment in relation to Other medication

It is important to distinguish between serious and severe AEs. Severity is a measure of intensity whereas seriousness is defined by the criteria in Section 6.3.3. An AE of severe intensity need not necessarily be considered serious. For example, nausea that persists for several hours may be considered severe nausea, but not a SAE. On the other hand, a stroke that results in only a limited degree of disability may be considered a mild stroke but would be a SAE.

#### Adverse Events based on signs and symptoms

When collecting AEs, the recording of diagnoses is preferred (when possible) to recording a list of signs and symptoms. However, if a diagnosis is known and there are other signs or symptoms that are not generally part of the diagnosis, the diagnosis and each sign or symptom will be recorded separately.

#### Adverse Events based on examinations and tests

Deterioration as compared to baseline in protocol-mandated vital signs should therefore only be reported as AEs if they fulfill any of the SAE criteria or are the reason for discontinuation of treatment with the investigational product.

If deterioration in a laboratory value/vital sign is associated with clinical signs and symptoms, the sign or symptom will be reported as an AE and the associated laboratory result/vital sign will be considered as additional information. Wherever possible the reporting investigator uses the clinical, rather than the laboratory term (eg, anemia versus low hemoglobin value). In the absence of clinical signs or symptoms, clinically relevant deteriorations in non-mandated parameters should be reported as AE(s).

Any new or aggravated clinically relevant abnormal medical finding at a physical examination as compared with the baseline assessment will be reported as an AE.

**Note:** Cases where a subject shows an AST **or** ALT  $\ge 3x$ ULN **or** total bilirubin  $\ge 2x$ ULN may need to be reported as SAEs, please refer to Appendix B 'Actions required in cases of combined increase of Aminotransferase and Total Bilirubin – Hy's Law', for further instructions.

#### **Disease progression**

Disease progression can be considered as a worsening of a subject's condition attributable to the disease for which the investigational product is being studied. It may be an increase in the severity of the disease under study and/or increases in the symptoms of the disease. The development of worsening urinary symptoms or metastases should be considered as disease progression and not an AE. Events, which are unequivocally due to disease progression, should not be reported as an AE during the study.

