# 1.4 Rationale for conducting this study

The frequency of HRD in prostate cancer increases substantially from the population of patients with localized prostate cancer to those with metastatic disease, reflecting the lethal phenotype mediated by HRD. Lethality is a reflection of early micrometastatic dissemination and an inability of local therapy alone to cure the disease. Men with localized prostate cancer with HRD either as a result of germline or somatic inactivation require better systemic therapy to improve their outcomes. The primary objective of this study is to assess whether the use of the PARP inhibitor olaparib prior to prostatectomy will result in pCR, which is credentialed in other malignancies as a surrogate for effective systemic elimination of tumor and long term cure. This is a pilot study to assess the feasibility of this approach in men with localized disease, with assessment of pCR, surgical margin status, extracapsular extension, seminal vesicle and nodal involvement, all of which are pathologic indicators of activity of neoadjuvant therapy. It is anticipated that the majority of patients will be known to be carriers of pathogenic germline variants, although a subset with purely somatic inactivation and HRD may identified in other ways. There is no evidence that tumors with germline vs. somatic inactivation will be differentially sensitive to PARP inhibition, so both populations will be eligible. A neoadjuvant PARP inhibitor study has not been performed in patients with prostate cancer and this study will also assess the safety and toxicity of olaparib in this patient population. If neoadjuvant therapy does not result in pCR, the remaining tissue is by definition resistant to therapy and remaining tumor tissue will be interrogated for mechanisms of resistance to inform future combination studies in advanced and localized HRD prostate cancer.

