Starting on Day 1, all patients will ingest olaparib (300 mg twice daily) at the same times each day, without breaks (except as outlined for toxicity), for 90 days. The 90 day duration is chosen as a duration adequate to assess impact of neoadjuvant therapy on downstaging but not so prolonged that if patients do not respond to therapy, that potentially curative local therapy is being significantly delayed. Multiple studies have demonstrated in unselected populations that 90 day delay to surgery is not associated with any change in long term outcomes . During neoadjuvant therapy, dose reduction of olaparib is allowed for toxicity as detailed in the protocol. Patients should receive olaparib until 1 day prior to prostatectomy, until the

patient can no longer tolerate the treatment due to an adverse event, until the patient initiates another systemic antineoplastic drug or an investigational drug, or at the discretion of the Investigator. Safety and tolerability will be documented throughout the study and 30 days after prostatectomy by assessment of adverse events, vital signs, and laboratory assessments as defined in the Schedule of Activities. All adverse events will be monitored and recorded until the Safety Follow-up visit. Adverse events will be graded according to the National Cancer Institute Common Terminology Criteria for Adverse Events, Version 4.03 (NCI-CTCAE v4.03). In the event a patient discontinues olaparib due to a related adverse event, follow up will continue until adequate resolution of the adverse event, the physician deems the adverse event to be stable, the patient initiates another systemic antineoplastic drug or an investigational drug, or the patient withdraws consent from the study. A safety follow-up visit will be conducted approximately 30 days after the last dose of olaparib or before the initiation of a new systemic antineoplastic therapy or investigational agent, whichever occurs first. Any ongoing adverse event thought to be related to study treatment will be followed until the event has resolved to baseline grade, the event is assessed by the Investigator as stable, the patient initiates another systemic antineoplastic drug or an investigational drug, the patient is lost to follow-up, the patient withdraws consent, or it has been determined that study treatment or participation is not the cause of the adverse event.

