## 5.4.12.3 Interruptions for intercurrent non-toxicity related events

Study treatment dose interruption for conditions other than toxicity resolution should be kept as short as possible. If a patient cannot restart study treatment within 4 weeks for resolution of intercurrent conditions not related to disease progression or toxicity, the case should be discussed with AZ study physician.

All dose reductions and interruptions (including any missed doses), and the reasons for the reductions/interruptions are to be recorded in the eCRF.

Study treatment should be stopped 1 day before prostatectomy. No stoppage of study treatment is required for any needle biopsy procedure.

Study treatment should be discontinued for a minimum of 3 days before a patient undergoes radiation treatment. Study treatment should be restarted within 4 weeks as long as any bone marrow toxicity has recovered.

Because the AEs related to olaparib may include asthenia, fatigue and dizziness, patients should be advised to use caution while driving or using machinery if these symptoms occur.

Table 4 Dose reductions for study treatment

Initial Dose	Following re-challenge post interruption: Dose reduction 1	Dose reduction 2
300mg twice daily	250mg twice daily	200mg twice daily

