## Time period for collection of adverse events

Adverse events and SAE will be collected from the time of patient consent until 30 days after prostatectomy.

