# \* Send SAE report and accompanying cover page by way of Email to [contact] or by fax to AstraZeneca's designated fax line:

If a non-serious AE becomes serious, this and other relevant follow-up information must also be provided to AstraZeneca and the FDA.

Serious adverse events that do not require expedited reporting to the FDA need to be reported to AstraZeneca preferably using the MedDRA coding language for serious adverse events. This information should be reported on a monthly basis and under no circumstance less frequently than quarterly.

All SAEs have to be reported to AstraZeneca, whether or not considered causally related to the investigational product. All SAEs will be documented. The investigator is responsible for informing the IRB and/or the Regulatory Authority of the SAE as per local requirements.

Non-serious adverse events and SAEs will be collected from the time study drug is given, throughout the treatment period and up to and including the 30 day follow-up period. After withdrawal from treatment, subjects must be followed-up for all existing and new AEs for 30 calendar days after the last dose of trial drug and/or until event resolution. All new AEs occurring during that period must be recorded (if SAEs, then they must be reported to the FDA and AstraZeneca). All study-related toxicities/ SAEs must be followed until resolution, unless in the Investigator's opinion, the condition is unlikely to resolve due to the patient's underlying disease.

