## 11.3 Methods of statistical analysis

Statistical analyses will be performed using all patients with evaluable data (e.g., pathologic staging among those who had a prostatectomy, and safety data among those who receive a dose of olaparib).

For efficacy analysis pathologic complete response is defined as the absence of morphologically identifiable carcinoma in the prostatectomy specimen, as evaluated by the site pathologist using standard methods. Formalin-fixed, paraffin-embedded slides will be evaluated by a central pathology review at completion of the study. Comparison of the actual pathologic complete response rate with the historial rate of 10%.

For safety analyses, all patients who received at least one dose of study drug and had at least one post-baseline safety assessment will be evaluated. Data will be descriptive, describing frequency of grade 1-5 adverse events. Data from all cycles of treatment will be combined in the presentation of safety data. AE will be listed individually by subject. The number of subjects experiencing each AE will be summarized by the Medical Dictionary for Regulatory Activities (MedDRA) system organ class, MedDRA preferred term and CTCAE grade. The number and percentage of subjects with adverse events in different categories (e.g. causally related, CTCAE grade ≥3 etc.) will be summarized. Any AE occurring before the first dose of investigational product (i.e. before study Day 1) will be included in the data listings but will not be included in the summary tables of adverse events. Any AE occurring within the defined 90 day follow-up period after discontinuation of olaparib will be included in the AE summaries. Hematology, clinical chemistry, vital signs, ECG data, demographic data, medical histories and concomitant medications will be listed individually by subject. For all laboratory variables, which are included in the current version of CTCAE, the CTCAE grade will be calculated. Summary statistics of mean, median, standard deviation, minimum, maximum and number of observations will be used. Details of any deaths will be listed for all subjects.

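### The rule that worsening urinary symptoms are progression and not AEs conflicts with the text around it, and can leave surgery- or drug-related urinary symptoms unrecorded or inconsistently recorded

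*Combined protocol and SAP*

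**What the plan says.** The instruction stands in the unnumbered paragraph Disease progression, within section 6.3.4: "The development of worsening urinary symptoms or metastases should be considered as disease progression and not an AE". The same paragraph opens by defining progression as a "worsening of a subject's condition attributable to the disease for which the investigational product is being studied". It closes by withholding from AE reporting only those events that are beyond doubt the result of progression.

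Section 6.3.4, Time period for collection of adverse events, sets the window: "Adverse events and SAE will be collected from the time of patient consent until 30 days after prostatectomy". Section 3.2 agrees: "Safety and tolerability will be documented throughout the study and 30 days after prostatectomy by assessment of adverse events". Section 6.3.5 counts from the drug instead: "subjects must be followed-up for all existing and new AEs for 30 calendar days after the last dose of trial drug". For the tables, section 11.3 says: "Any AE occurring within the defined 90 day follow-up period after discontinuation of olaparib will be included in the AE summaries".

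Section 6.3.1 defines an AE without regard to whether the product caused it. Section 6.3.3 defines an SAE as an AE that meets further criteria.

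**The concern.** Read alone, the urinary sentence settles the classification before anyone asks about cause. It puts a non-specific symptom beside metastasis, which is progression by nature. It does not ask for evidence of tumour growth, and it does not stop at surgery. Yet prostatectomy is planned for every man and falls inside the AE window. Once the prostate is out, local tumour is a less plausible cause of new urinary symptoms than the operation.

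At stake is the completeness of the safety description. Section 1.4 notes that no neoadjuvant PARP-inhibitor study has been done in prostate cancer and adds that "this study will also assess the safety and toxicity of olaparib in this patient population". On perioperative complications, section 1.5 can point only to breast cancer studies. Because an SAE must first be an AE, a symptom declared not to be an AE also escapes SAE reporting.

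**Working it through.** The plan gives no figure on this point, so the check is mainly a comparison of texts.

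**1. Inside the paragraph.** The first sentence requires that the worsening be attributable to the disease. The second speaks of greater severity or more symptoms of that disease. The third, on urinary symptoms, has no such condition. The fourth requires certainty about the cause before an event goes unreported. A urinary symptom caused by surgery fails the first and fourth tests but meets the third as worded. The paragraph therefore gives two answers for the same event.

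**2. Against the AE definition.** Section 6.3.1 makes any new or worsened undesirable condition an AE, whatever its cause. The urinary sentence takes one type of worsening out of that definition and does not say that it is an exception.

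**3. Does the window reach past surgery?** Section 5.4.12.3 says: "Study treatment should be stopped 1 day before prostatectomy". So:
- Sections 3.2 and 6.3.4: postoperative day 30.
- Section 6.3.5: 30 days after the last dose, and 30 − 1 = 29, so about postoperative day 29.
- Section 11.3: 90 days after discontinuation, and 90 − 1 = 89, so about postoperative day 89 if the drug is stopped on schedule.

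All three cover early recovery. The end-of-study visit at Day 120 (section 5.4.5) includes an AE review, so these symptoms would come up at a scheduled contact.

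**4. What stays reportable in any case.** In section 6.3.4, Adverse Events based on signs and symptoms prefers diagnoses to symptoms, so a diagnosed complication is not covered by the urinary sentence. Adverse Events based on examinations and tests makes a clinically relevant new or worse examination finding an AE.

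**5. What these routes may miss.** A symptom that the patient reports, without a diagnosis or an examination finding, is caught by neither. The paragraph Lack of efficacy settles doubtful deterioration of the cancer towards not being an AE. Apart from local regulations, its only exception is a contribution from study treatment; surgery is not mentioned.

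**6. Would an omission show later?** Table 6 has no urinary symptom scale. The variables listed in section 6.3.4 include causality to study procedures for SAEs only; other AEs are rated against the investigational product alone. Section 11.3 plans no urinary or surgical summary. Nothing planned would bring back an event set aside as progression.

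**7. Illustrative ceiling.** Inputs: 15 men (the target in section 11.2) and an assumed 10% to 50% with new or worse urinary symptoms after surgery. The documents give no rate.
- 15 × 0.10 = 1.5 men; 15 × 0.50 = 7.5 men.
- One unrecorded serious event: 1/15 = 6.7 percentage points on the SAE rate.

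The range assumes that every such symptom is classed as progression. The 6.7 points assume a safety set of 15. Section 11.1.2 counts everyone dosed and evaluable for toxicity, and replacement is allowed, so the set may be larger and the share per event smaller.

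**The case against.** A reader might infer that perioperative urinary toxicity is removed from the safety results. The documents do not support that. The paragraph as a whole limits progression to worsening caused by the cancer and withholds only certain cases, so an investigator who reads all of it would report a surgical urinary symptom. If postoperative symptoms are mostly surgical, they fail both limits. Diagnoses and examination findings remain AEs, hospitalization remains an SAE criterion, and SAE causality is rated against study procedures. The urinary system does not drop out of the tables. All of this stands.

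It can also be said that the safety aim concerns olaparib and not surgical morbidity, that Table 1 lists no urinary symptom reaction, and that a single arm with descriptive safety data cannot separate a drug effect from the effect of prostatectomy. These points limit what complete recording could show. They do not justify a rule that decides attribution before the data are collected: an event never recorded cannot be attributed to anything.

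What the objection does not remove is the conflict. Staff who look up how to record a urinary symptom find one direct instruction, and it is the one without the attribution condition.

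**Conclusion.** The urinary sentence contradicts the attribution limits in its own paragraph and the cause-independent AE definition in section 6.3.1. Since AE collection continues past prostatectomy, following it literally can leave surgery- or drug-related urinary symptoms out of the AE and SAE tables, and different readers can record the same event differently. The loss is possible, not certain.

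Its size cannot be estimated from the documents. The 1.5 to 7.5 men of 15 are a ceiling that rests on an assumed rate and on every case being classed as progression. Under the attribution limits, only symptoms unequivocally due to the cancer would be left out. The primary pCR analysis is not affected. The correction is worth making because it is cheap and because the planned data would not reveal an omission.

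**What to change.** Limit the sentence to urinary worsening that is unequivocally attributable to prostate cancer progression. Add that all other new or worsened urinary symptoms after the first dose, including those after prostatectomy, are recorded as AEs with CTCAE grade and attribution to olaparib, procedure or disease. The AE form then needs procedure and disease attribution for non-serious events too, at least for urinary ones.

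The cost is a one-sentence correction with one added statement, a few more AE entries for about 15 men, and a slightly higher reported AE rate. Only recording changes, not patient care. The three AE windows in sections 6.3.4, 6.3.5 and 11.3 also need to be reconciled; that is a separate matter, and this point holds under any of them.

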#### **Deaths**

All deaths that occur during the study, or within the protocol-defined 30-day post-study follow-up period after the administration of the last dose of study treatment, must be reported as follows:

Death clearly the result of disease progression should be reported to the study monitor at the next monitoring visit and should be documented in the eCRF but should not be reported as an SAE

Where death is not due (or not clearly due) to progression of the disease under study, the AE causing the death must be reported to the study monitor as a SAE within **24 hours** (see Section 6.3.5 for further details). The report should contain a comment regarding the co-involvement of progression of disease, if appropriate, and should assign main and contributory causes of death. This information can be captured in the 'death eCRF'.

Deaths with an unknown cause should always be reported as a SAE. A post mortem maybe helpful in the assessment of the cause of death, and if performed a copy of the post-mortem results should be forwarded to AstraZeneca within the usual timeframes.

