## 11. STATISTICAL METHODS AND SAMPLE SIZE DETERMINATION

### 11.1 Description of analysis sets

#### 11.1.1 Efficacy Analysis Set

Patients who receive olaparib for the complete planned neoadjuvant cycle and proceed to prostatectomy with tissue available for analysis of pathologic endpoints will be the efficacy analysis set. Patients who do not complete the treatment regimen or do not proceed to prostatectomy may be replaced in order to reach the target accrual for efficacy after discussion with principal investigator and sponsor

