## 11.2 Determination of sample size

This is a pilot study assessing whether PARP inhibition with olaparib has the capacity to induce high pathologic complete respone (pCR) rates in men with tumors harboring DNA repair deficiencies (i.e. induce synthetic lethality). The primary efficacy endpoint will be the pCR rate as determined on prostatectomy specimens following 12-weeks of neoadjuvant olaparib. The historical complete response rate to 3-8 months of androgen deprivation with LHRH agonist and androgen receptor antagonist is  $\sim 10\%$  (H0). We anticipate a complete response rate of  $\geq 40\%$  (H1) following 12-weeks of olaparib in patients with homologous DNA repair deficient tumors (truncal mutations/copy loss). Therefore, a sample size of 15 patients would yield 80% power to detect a difference between the null and alternative pathologic complete response rates at a two-sided alpha = 0.05

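### Non-fatal progression or a lost prostatectomy during neoadjuvant olaparib has no planned count, and men who miss the full course or surgery because of it can be replaced, which biases pCR upward

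*Combined protocol and SAP*

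**What the plan says.** **Reporting of progression.** Section 6.3.4 (Disease progression) treats worsening urinary symptoms and metastases as progression and adds: "Events, which are unequivocally due to disease progression, should not be reported as an AE during the study". The New cancers paragraph repeats this for metastasis, as AE or SAE. Under Deaths, "Death clearly the result of disease progression should be reported to the study monitor at the next monitoring visit"; such a death goes in the eCRF but is not an SAE.

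**Endpoints and outputs.** Section 2 lists pCR, surgical pathology (margins, extracapsular extension, seminal vesicles, nodes) and resistance mechanisms. Section 10.1 derives pathology variables. Section 11.3 plans a comparison of pCR with 10%, AE, laboratory and vital-sign outputs, and a listing of deaths.

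**Who is analysed.** Section 11.1.1 requires the complete olaparib course, prostatectomy and available tissue. It continues: "Patients who do not complete the treatment regimen or do not proceed to prostatectomy may be replaced", after discussion with the principal investigator and sponsor. Three other places differ:
- Section 5.4.6 leaves replacement of men who discontinue early to the investigator.
- Section 5.8 says that men unable to receive more than 6 weeks of olaparib will be replaced.
- Section 11.3 analyses everyone with evaluable data, such as pathology in all men who had surgery.

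**The delay.** Section 3.2 chose 90 days as not so long that, in men who do not respond, "potentially curative local therapy is being significantly delayed". It relies on studies in unselected populations. Section 1.5 describes HRD disease as aggressive and says long-term outcomes will not be formally evaluated.

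**The concern.** Each rule is ordinary in isolation; the gap appears when they are combined. Take a man who develops metastases on treatment and does not go to surgery. His progression is not an AE, so the AE tables do not show it. He has no specimen, so the primary and secondary endpoints do not show it. He is outside the section 11.1.1 set and may be replaced by another man who completes.

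Two things are at stake. The first is descriptive: the report could not say how many dosed men progressed or lost surgery before the planned operation. Since the reassurance about delay in section 3.2 comes from unselected men, that count is of direct interest here. The second is bias: these men are treatment failures, and removing them from the denominator can only raise the pCR rate. Correcting the denominator alone would not supply the count or the reasons, so both need attention.

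**Working it through.** **1. The plan's own figure.** Inputs from section 11.2: H0 10%, H1 40%, "two-sided alpha = 0.05", and "a sample size of 15 patients would yield 80% power to detect a difference". No test is named.
- Arcsine formula: h = 2·asin(√0.40) − 2·asin(√0.10) = 0.726; n = ((1.960 + 0.842)/0.726)² = 14.9, so 15, with power 80.3%. The stated figure reproduces.
- Exact binomial, n = 15: requiring at least 5 pCRs gives one-sided error P(X ≥ 5 | 15, 0.10) = 0.0127 and power 78.3%. Requiring at least 4 gives 0.0556. The working rule below is therefore 5 of 15.

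**2. Effect on the estimate.** Assumption: k dosed men progress, miss the full course or surgery, are replaced, and would be non-pCR if kept. The documents give no rate, so k is varied. With 5 pCRs in the final 15 completers, the section 11.1.1 result is 5/15 whatever k is.

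| k | All dosed | Rate | Exact one-sided p against 10% |
|---|---|---|---|
| 0 | 5/15 | 33.3% | 0.0127 |
| 1 | 5/16 | 31.3% | 0.0170 |
| 2 | 5/17 | 29.4% | 0.0221 |
| 3 | 5/18 | 27.8% | 0.0282 |
| 5 | 5/20 | 25.0% | 0.0432 |

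Whether 5/18 is significant at two-sided 0.05 depends on a convention that the plan does not state:
- Doubling the tail gives 2 × 0.0282 = 0.0564, not significant.
- The minimum-likelihood exact test gives 0.028, significant, because P(X = 0) = 0.15 exceeds P(X = 5) = 0.022 and the lower tail adds nothing.

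**3. Effect on type I error.** Suppose a fraction d of dosed men is excluded this way, all non-pCR, and the true rate in all dosed men is 10%. The rate among the remaining men is 0.10/(1 − d).
- d = 10%: 0.111, so P(X ≥ 5 | 15) = 0.0195.
- d = 20%: 0.125, giving 0.0311.
- d = 25%: 0.133, giving 0.0398.

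The value at d = 0 is 0.0127. Likewise, a 40% rate among completers corresponds to 0.40 × (1 − d) = 36%, 32% and 30% of all dosed men.

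**4. What the missing count would show.** With k = 2, the table would read 2/17 = 11.8% (exact 95% CI 1.5% to 36.4%). With no events in 15 men the one-sided 95% upper limit is 1 − 0.05^(1/15) = 18.1%.

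**5. Where a man who progresses appears.**

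| Case | In the section 11.1.1 set? | In a planned output? |
|---|---|---|
| Progresses, completes olaparib, has surgery with tissue | Yes; non-pCR if carcinoma is found | Yes: pCR and surgical pathology |
| Progresses, alive, misses the full course but has surgery | No; may be replaced | Pathology under section 11.3, in conflict with 11.1.1; progression itself not counted |
| Progresses or becomes inoperable, alive, no surgery | No; may be replaced | No count of the progression or lost surgery |
| Dies of progression | No, if there is no surgery | Death listing, section 11.3 |

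**The case against.** A reader might infer that any man who progresses is excluded and that progression is counted nowhere. The documents do not support that. Section 11.1.1 tests course, surgery and tissue, not progression, and section 5.7 does not list progression as a reason to stop olaparib. The secondary pathology endpoints record advanced disease in operated men. Deaths from progression enter the eCRF, and all deaths are listed. PSA is measured at days 30, 60 and 90. Under Lack of efficacy, deterioration can be an AE if study treatment is thought to have contributed. All of this stands, but none of it gives a count of living men who progressed or lost surgery.

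A reader might also call this the main harm of the design. The protocol does not say so: it presents 90 days as short enough to avoid significant delay. One may ask whether data from unselected men carry over to HRD disease, but the ranking would be a judgement.

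Nor do the figures show that a positive result would be overturned. Two such men leave p at 0.022, or 0.044 when doubled, still below 0.05. Three of 18 (17%) is an assumed rate with no source in the documents, and significance is then lost only under the doubled-tail convention.

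Finally, replacement is discretionary in section 11.1.1, and section 11.3 can be read as keeping every operated man. That is fair, but it leaves the population unsettled, and neither reading keeps a man without surgery in the denominator. In a 15-man uncontrolled pilot the count will be imprecise; it is still worth reporting.

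**Conclusion.** The point holds in a limited form. Non-fatal progression, loss of operability and missed prostatectomy have no planned count. Following section 11.1.1 removes, and allows replacement of, men whose disease costs them the full course or surgery, and the direction of the resulting pCR bias is upward. The size is unknown because the documents give no rate. Under the assumed losses it is about 4 to 6 percentage points for two or three men (33% to 29% or 28%), and the type I error of the 5-of-15 rule rises from 0.013 to 0.031 at 20% exclusion. These figures assume that every excluded man is non-pCR and that the comparison with 10% is an exact binomial test. This is an inexpensive improvement to a pilot; it does not show that the trial's conclusion would change.

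**What to change.** - **Sections 11.1.1 and 11.3:** make the main pCR analysis over all men who received at least one dose. Count as non-pCR those who progress, become inoperable or have no prostatectomy because of their disease. Replacement should not take them out of the denominator. State how men who miss surgery for unrelated reasons are handled. Keep the completer analysis as supportive.
- **Section 11.3:** add one table in all dosed men giving the number, with exact 95% CI, who progressed, became inoperable or did not have the planned prostatectomy, with the reason. State what counts as progression for this table, since section 6.3.4 describes it only in general terms. Name the test of pCR against 10% and its two-sided convention.
- **Reconcile** sections 5.4.6, 5.8, 11.1.1 and 11.3 on who is analysed and who is replaced. Also reconcile, within section 6.3.4, the instruction to report new or aggravated examination findings as AEs with the exclusion of progression. The AE coding rule for progression can stay.

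**Cost:** protocol wording, one table, and possibly one CRF field for why surgery did not occur. Documentation in the eCRF is stated only for deaths from progression, and the section 5.4 visit lists contain no progression or operability item, so existing capture should not be assumed. The reported pCR rate may be slightly lower.
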